As demonstrated in the PoC Study CCFZ533X2203 in pSS, a single s.c. dose of 600 mg iscalimab at Day 1 will deliver plasma concentrations generally above 40 µg/mL after 1 week. Subsequent weekly doses on Week 61 and 62 in Arms 1 and 2 are expected (i) to maintain CFZ533 plasma levels above 40 µg/mL, and (ii) to deliver iscalimab trough levels that are close to expected steady state conditions.

Further supportive arguments on the selected loading dosing regimen are provided in the Rationale for dose/regimen and duration of treatment of the TWINSS core study protocol (refer to Section 4 of the core study protocol).

Rationale for maintenance regimen

The maintenance regimen of 600 mg s.c. Q2W is expected to provide a median steady state trough plasma level at about 144 µg/mL (90% of the population within 282 - 46 µg/mL), in the upper range of trough levels observed in the PoC Study CCFZ533X2203-Cohort 2 (i.v. regimen; these concentrations were associated with clinical efficacy and suppression of a biologically relevant biomarker CXCL13 - a marker of germinal center activity).

The maintenance regimen of 300 mg s.c. Q2W is expected to deliver a median steady state trough plasma level at about 54 µg/mL (90% of the population within 125 - 0.1 µg/mL), with a reasonable chance to show efficacy in SjS.

The between subject variability in exposure within the two treatment arms (to a lesser extent in the 600 mg treatment arm) is likely to depend on the biology of CD40 in target tissues (expression level, turnover) and its potential modulation during the treatment period.

Rationale for the duration of the safety follow-up period (target engagement after the last dose)

Based on predicted median CFZ533 plasma concentration-time profile at 600 mg s.c. Q2W regimen, at about 14 weeks after the last dose, iscalimab plasma concentrations are expected to drop below 20 µg/mL with no expected pharmacodynamic activity in target tissues (e.g., germinal centers; data from non-human primates - please see current IB).

A 12-week follow-up period (14 weeks after the last dose) has been selected for the study and is justified to monitor for any related serious adverse events (SAE).

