Novartis will provide to investigators in a separate document a proposed informed consent form that complies with the ICH GCP guidelines and regulatory requirements and is considered appropriate for this study. Any changes to the proposed consent form suggested by the investigator must be agreed by Novartis before submission to the IRB/IEC.

Information about common side effects already known about the investigational drug can be found in the IB. This information will be included in the participant informed consent and should be discussed with the participant during the study as needed. Any new information regarding the safety profile of the investigational drug that is identified between IB updates will be communicated as appropriate, for example, via an investigator notification or an aggregate safety finding. New information might require an update to the informed consent and then must be discussed with the participant.

Women of child bearing potential must be informed that taking the study treatment may involve unknown risks to the fetus if pregnancy were to occur during the study and agree that in order to participate in the study they must adhere to the contraception requirements.

[REDACTED]

[REDACTED]

[REDACTED]

A copy of the approved version of all consent forms must be provided to Novartis after IRB/IEC approval.

Participants might be asked to complete an optional questionnaire to provide feedback on their clinical trial experience.

8 Visit schedule and assessments

The Assessment Schedule ([Table 8-1](#)) lists all of the assessments when they are performed. All data obtained from these assessments must be supported in the participant's source documentation.

Participants should be seen for all visits/assessments as outlined in the assessment schedule ([Table 8-1](#)) or as close to the designated day/time as possible.

Every efforts should be made to adhere to the weekly dosing schedule (loading doses) and the bi-weekly maintenance dosing regimen in both arms in this trial.

Visits can be performed with the following time windows:

Treatment Period

- +/- 1 calendar day: from Week 60E1 (Day 421) to Week 61 (Day 428)
- +/- 2 calendar days: from Week 62 (Day 435) to Week 66 (Day 463)
- +/- 5 calendar days: from Week 68 (Day 477) to Week 108 (Day 757)

Follow-up Period

+/- 5 calendar days from Week 112 (Day 785) to Week 120 (Day 841)

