^X Assessment to be recorded in the clinical database or received electronically from a vendor

¹ Corresponds to the Week 60 visit of the core study. Assessments carried out as part of Week 60 as per core study protocol should be used for Week 60E1 of the extension study.

² Optional site visits - Week 66, 70, 74, 78, 82, 86, 90, 94, 98, 102, 106. Participants who are unable to self-administer the PFS injections at home will visit the site and site staff will supervise self-administration or administer the PFS injection for them. Other participants who can self-administer the PFS injection can do so at home at these optional visits.

³ Informed consent should be obtained before commencement of the Week 60 assessments of the core study.

⁴ Contact IRT for new treatment reassignment.

⁵ AEs/SAEs occurring after the participant has signed the informed consent must be captured on the appropriate eCRF page.

⁶ C - These assessments shall be conducted as part of the core study CCFZ533B2201 and will not be repeated in this extension study

⁷ S - Assessment to be recorded in the source documentation only

⁸ [REDACTED]

⁹ Local lab testing of CMV IgG, IgM and DNA (by PCR) must be performed every 3 months until end of study. Hepatitis B monitoring applicable to HBsAg (-) patients who were HBcAb (+) and HBV DNA (-) at screening during the core study. Local lab testing of HBsAg and HBV DNA must be performed every 3 months until end of study.

¹⁰ While on treatment, coagulation monitoring applies only to participants who have antiphospholipid antibodies (lupus anticoagulant, anti-cardiolipin antibodies) and/or who are on pre-existing antithrombotic therapy/prophylaxis, as reflected in the exclusion criteria of the TWINSS core study protocol.

¹¹ Analysis of cryoglobulins will be done only for participants who were positive at screening in the TWINSS core study.

¹² Urine pregnancy tests will be performed throughout the study

¹³ Blood sample is collected pre-dose.

¹⁴ [REDACTED]

¹⁵ [REDACTED]

¹⁶ Optional [REDACTED]

¹⁷ [REDACTED]

¹⁸ [REDACTED]

¹⁹ In case of premature discontinuation, participants will enter the follow-up after completing assessments for this visit.

²⁰ Mandatory to all participants, including those who have discontinued the study prematurely.

²¹ Week 106 is the last dose administration visit in the Treatment Period.

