2.1.1.2 Study Day 1 and other study days

The first day of administration of study treatment in extension study is defined as Study Day 1 or Day 1.

All other study days will be labeled relative to Day 1. For event dates on or after Day 1, study day for a particular event date is calculated as [Date of event] – [Date of first dose]+1, i.e., Day 2, Day 3, etc., will be one day, two days, etc., after Day 1, respectively. For the dates before Day 1, study day for an event date is calculated as [Date of event] – [Date of first dose], i.e., Day -1, Day -2, etc., will be one day, two days, etc., before Day 1, respectively. Duration of an event will be calculated as (Event end date – Event start date + 1).

The descriptor "Day 0" will not be used.

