2.3 Treatments (study treatment, rescue medication, concomitant therapies, compliance)

2.3.1 Study treatment / compliance

The analysis of study treatment data will be based on the safety set.

Duration of exposure will be defined as the time from first dose of study medication to the last dose date plus 14 days.

For subjects who completed treatment, there is a visit window of \pm 5 days for the 14 days. For subjects who discontinued treatment, the EoT disposition date is the last assessment date in treatment period. Therefore, the EoT visit was not considered ideal for the end of exposure calculation and the current exposure calculation method is proposed:

Duration of exposure (days) = (last dose date + 14 days) - first dose date +1

Duration of exposure (weeks) = duration of exposure (days) / 7

The number and percentage of patients in SAF who are exposed to study treatment for prespecified time intervals (every two weeks) will be summarized for the overall study. Patients who receive any wrong study medications will be listed.

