2.4 Safety analyses

All safety endpoints (i.e., adverse events, laboratory data, and vital signs in extension study will be summarized by treatment for all subjects of the safety set.

Adverse events (AEs)

All adverse events in extension study are summarized based on treatment emergent only. The definition for "treatment emergent" is as below:

TEAE includes all events up to the last dose date plus 14 weeks (98 days) or the end of the entire study period (including the safety follow-up period), whichever occurred earlier. A listing of all adverse events during the study will be produced, with those defined as TEAE for the study treatment period with "treatment emergent" flag displayed.

The number and percentage of patients with treatment emergent adverse event (TEAE) will be summarized for the following:

- by treatment, primary system organ class and preferred term
- by treatment, primary system organ class, preferred term and maximum severity
- by treatment, Standardized MedDRA Query (SMQ) and preferred term.

Summaries will also be provided for study treatment related adverse events, serious adverse events, treatment related serious adverse events, deaths, and adverse events leading to permanent discontinuation of study-drug.

If a particular AE 'severity' is missing, this variable will be listed as missing and treated as missing in summaries. If a subject reported more than one adverse event with the same preferred term, the adverse event with the greatest severity will be presented. If a subject reported more than one adverse event within the same primary system organ class, the subject will be counted only once with the greatest severity at the system organ class level, where applicable.

The most common adverse events reported ($\geq 5\%$ in any group for each preferred term in the table by PT or $\geq 5\%$ in any group for each SMQ table) will be presented in descending frequency according to its incidence in all subjects starting from the most common event.

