4.3 Statistical models

4.3.1 Analysis of binary (and categorical) data

4.3.1.1 Summary statistics

Summary statistics for discrete variables will be presented in contingency tables and will include absolute and relative frequencies. If applicable, confidence intervals will be derived as well based on the score method including continuity correction [Newcombe (1998)]:

With *z* as (1-alpha/2)-quantile of the standard normal distribution (SAS: z=PROBIT(1-alpha/2), *n* as total number of subjects (i.e. number of subjects in the denominator), and *p* as estimated crude incidence (number of subjects with event / *n*) it is q = 1 - p

Then the lower limit is for p > 0, (L = 0 for p = 0),

$$L = \max\left(0, \frac{2np + z^2 - 1 - z\sqrt{z^2 - 2 - \frac{1}{n} + 4p(nq + 1)}}{2(n + z^2)}\right)$$

and the upper limit is for p < 1, (U = 1 for p = 1),

$$U = \min\left(1, \frac{2np + z^{2} + 1 + z\sqrt{z^{2} + 2 - \frac{1}{n} + 4p(nq - 1)}}{2(n + z^{2})}\right).$$

For response variables the placebo adjusted response rates (risk difference) including 95% confidence interval will be derived by visit.

5 Reference

Newcombe RG (1998) Two-sided confidence intervals for the single proportion: comparison of seven methods. Statistics in Medicine; 17: 857-872.

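### TEAEs are planned only as crude percentages although time at risk depends on when treatment stops; exposure-adjusted rates should stand beside them

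*SAP*

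**What the plan says.** TEAEs and SAEs are listed first among the primary endpoints (Protocol Table 2-1, SAP Table 1-1). SAP 2.4 sets out how they are reported: "The number and percentage of patients with treatment emergent adverse event (TEAE) will be summarized for the following", with splits by system organ class, preferred term, maximum severity and SMQ. Protocol 12.4.2 likewise gives only numbers and percentages. SAP 4.3.1.1 treats a proportion "as estimated crude incidence", meaning subjects with the event divided by all subjects in the denominator.

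The window is individual: "TEAE includes all events up to the last dose date plus 14 weeks (98 days) or the end of the entire study period", whichever comes first. SAP 2.4 does not state when the window opens; the start at first dose comes from Protocol 12.4.2.

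Exposure is tabulated separately and on a different clock: "Duration of exposure will be defined as the time from first dose of study medication to the last dose date plus 14 days" (SAP 2.3.1). The disclosure tables (SAP 2.4.1) add occurrence counts, again without a time denominator. No readable text in either document mentions participant-years, an exposure-adjusted rate or time to first event for adverse events. For events of special interest the SAP says that they will be summarized but names no measure, and the list of events is missing from the text as read.

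**The concern.** A crude percentage treats every participant as observed for the same time. Here someone who stops early leaves the TEAE risk set early, even if that person stays in the study. Protocol Table 6-2 keeps some discontinuers on the visit schedule, but their events later than 98 days after the last dose do not count as treatment-emergent.

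Unequal stopping between arms is plausible. Under the algorithm in Protocol 6.1.3 every core-study non-responder goes to 600 mg, while the 300 mg arm receives only responders. Protocol 6.2 requires study medication to stop when escape treatment is needed, and that may fall more often on the arm holding the non-responders.

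The two dose columns will be read side by side. Protocol 1.2 says the safety data may inform Phase III design, and Protocol 4.3 says that two doses are used so that both can be evaluated for safety. If one arm stops earlier, its percentages will look better than its event rate.

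**Working it through.** **Calendar.** Inputs: "The first day of administration of study treatment in extension study is defined as Study Day 1 or Day 1" (SAP 2.1.1.2); "Week 106 is the last dose administration visit in the Treatment Period" (footnote 21 to the assessment schedule, Protocol Table 8-1); "A 12-week follow-up period (14 weeks after the last dose) has been selected for the study" (Protocol 4.2).

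- First dose: Week 60E1 = extension Day 1.
- Last planned dose: Week 106 = (106 − 60) × 7 + 1 = Day 323.
- Window end for a completer: 323 + 98 = Day 421.
- The plan's own figure: SAP Table 2-1 puts Week 120 at Day 421, and (120 − 60) × 7 + 1 = 421. The two agree.
- Window after a single dose: 1 + 98 = 99 days.
- Ratio of the extremes: 421 / 99 = 4.25.

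The ratio falls quickly with later stopping:

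| Last dose (day) | Time at risk (days) | 421 / time at risk |
|---|---|---|
| 1 | 99 | 4.25 |
| 29 | 127 | 3.31 |
| 113 | 211 | 2.00 |
| 225 | 323 | 1.30 |
| 323 | 421 | 1.00 |

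**Effect on an arm's percentage.** The documents give neither event rates nor discontinuation rates, so what follows rests on assumptions: a constant rate λ = 0.3 first events per year in both arms; drop-outs' last dose spread evenly over Days 1 to 323; and stopping unrelated to the event counted.

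- Probability of an event within T days: 1 − exp(−λT / 365.25).
- Completers: 1 − exp(−0.3 × 421 / 365.25) = 29.23%.
- Drop-outs: the average of 1 − exp(−0.3 × (s + 98) / 365.25) over s = 1 to 323 is 18.99%.
- Arm with drop-out d: crude % = (1 − d) × 29.23 + d × 18.99.
- Mean drop-out window: 162 + 98 = 260 days. Arm mean = (1 − d) × 421 + d × 260.

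| Drop-out | Crude % | Mean days at risk | Gap from the 10% arm (points) | Ratio of mean days, 10% arm to this arm |
|---|---|---|---|---|
| 10% | 28.2 | 404.9 | 0 | 1.00 |
| 20% | 27.2 | 388.8 | 1.0 | 1.04 |
| 30% | 26.2 | 372.7 | 2.0 | 1.09 |
| 40% | 25.1 | 356.6 | 3.1 | 1.14 |

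In the same model, participants with an event divided by time to first event or window end gives 0.30 per year in every row.

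**Wider range.** For 10% v 30% drop-out and rates from 0.1 to 2.0 per year, the gap is 0.9 to 4.2 points when stopping is spread evenly over the dosing visits. It is 1.6 to 9.6 points when stopping falls within the first four doses or after the first dose. Equal drop-out with the same timing gives zero throughout.

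**The case against.** **The fourfold range is the extreme.** A reader might infer from 99 v 421 days that the arm percentages are badly distorted. They are not. What matters is mean time at risk per arm, which differs by a factor of 1.04 to 1.14 in the scenarios tabulated above. For scale, if the 206 enrolled (SAP 1.1) split into two arms of 103 (an assumption), the standard error of a difference near 27% is √(2 × 0.272 × 0.728 / 103), or about 6 points. This limits the size of the point. It does not remove it, because the gap is systematic rather than noise.

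**Unequal drop-out is an inference.** Entrants have completed 48 weeks of treatment and 12 weeks of follow-up, and the investigator expects them to benefit (Protocol 5.1). The 600 mg arm also holds 600 mg responders. Unequal stopping is therefore plausible, not established.

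**A masked excess is easy to overstate.** Suppose the true rate is 20% higher (0.36 per year) in an arm with 40% drop-out. It shows 29.3% against 28.2%, a ratio of 1.04. It is tempting to blame the whole fall from 1.20 on drop-out. With 10% drop-out in both arms the ratio is already 32.8 / 28.2 = 1.16, because a proportion saturates. Drop-out accounts only for the step from 1.16 to 1.04.

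**Direction depends on why people stop.** Protocol 9.1.1 requires stopping for severe or serious infections and for persistent neutropenia of grade 3 or higher. Those participants are already in the numerator for that event. Understatement in the arm that stops more therefore needs stopping for reasons other than the event counted. That condition belongs in the claim.

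**Context is already planned.** Exposure by arm, disposition with reasons, events leading to discontinuation and a flagged listing (SAP 2.2.1, 2.3.1, 2.4) would reveal unequal stopping. They would not correct for it. Exposure ends at last dose + 14 days, 84 days short of the uncapped TEAE window, and time to first event cannot be recovered from a count and an exposure table. The 98-day tail also helps: under the four-week tail in Protocol 12.4.2 the extreme ratio would be 351 / 29 = 12.1.

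**The study is descriptive and not randomized.** No test between arms is planned (SAP 2.1). A reader might infer that rates would make the arms fairly comparable. They would not, because dose is set by core-study dose and response.

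**Conclusion.** The point holds in limited form. The readable plan reports TEAEs only as crude percentages over windows that vary with the last dose, and nothing else in it supplies a time denominator. If stopping for other reasons differs between arms, the arm that stops earlier looks safer than its event rate warrants. At 0.3 events per year with even drop-out the gap is 1.0 point at 10% v 20% drop-out and 3.1 points at 10% v 40%. Across the wider assumed rates and earlier stopping it reaches 9.6 points at 10% v 30%. With equal drop-out of the same timing it is nil.

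These sizes rest on a constant hazard and on drop-out and event rates that the documents do not give. Crude percentages are a defensible convention in a descriptive extension, so this is a worthwhile addition, not an error to be put right. Redacted text may hold further adverse event summaries; none is visible.

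**What to change.** Add to SAP 2.4, beside the crude percentages and by extension arm, exposure-adjusted incidence rates per 100 participant-years. The numerator is participants with the event. The denominator is the sum of time from first dose to first event or, without an event, to the end of the TEAE window. Provide them for any TEAE, SAEs, infections and events of special interest.

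Add two sentences of interpretation. First, the rates remove only the time-at-risk artefact and leave the confounding from non-randomized, response-based assignment. Second, they assume a roughly constant hazard, so events that cluster early, such as injection reactions, should be read from the percentages or from a cumulative incidence.

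The cost is one more table or column, built from dates already needed for the TEAE flag. No new data are collected.

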2.4.1 Disclosure reporting

For the legal requirements of ClinicalTrials.gov and EudraCT, two required tables on treatment emergent AEs: non-SAEs with an incidence greater than 5%, and deaths and SAEs including events suspected to be related to study treatment, will be provided by treatment, SOC and PT on the Safety Set.

If, for the same patient, several consecutive AEs (irrespective of study treatment causality, seriousness and severity) occurred with the same SOC and PT:

- a single occurrence will be counted if there is ≤ 1 day gap between the end date of the preceding AE and the start date of the consecutive AE
- more than one occurrence will be counted if there is > 1 day gap between the end date of the preceding AE and the start date of the consecutive AE

For occurrence, the presence of at least one SAE / SAE suspected to be related to study treatment/ non-SAE has to be checked in a block e.g. among AE's in $a \le 1$ day gap block, if at least one SAE is occurring, then one occurrence is calculated for that SAE.

The number of deaths resulting from SAEs suspected to be related to study treatment and SAEs irrespective of study treatment relationship will be provided by SOC and PT.

These tables will be provided at the final analysis after all participants have completed the study.

Adverse events of special interest / grouping of AEs

Adverse events of special interest for the treatment will also be summarized. AEs of special

interest for CFZ533 treatment include the following, specified as compound-level risk factors defined in the Case Retrieval Strategy (eCRS). The search criteria in the latest eCRS corresponding the MedDRA version at the database lock will be used and reported in the CSR.

2.4.2 Deaths

Separate summary and listing will be provided for deaths.

2.4.3 Laboratory data

Only data from the central labs will be used for analysis in this section unless otherwise specified.

The summary of laboratory evaluations in extension study will be presented for two groups of laboratory tests (hematology and serum chemistry).

Descriptive summary statistics for the change from baseline to each study visit in extension study will be presented by laboratory test and treatment group. Change

Novartis	For business use only	Page 20
SAP Amendment 3		CCFZ533B2201E1

from baseline will only be summarized for subjects with both baseline and post baseline values and will be calculated as:

change from baseline = post baseline value – extension baseline value

For laboratory test values below Lower Level of Quantification (LLQ) or above Upper Level of Quantification (ULQ) will be imputed as LLQ or ULQ value, respectively. These laboratory values will be displayed in listings using the standard unit with the reported sign ("<" or ">")."

The following laboratory parameters will be analyzed with respect to numerical Common Terminology Criteria for Adverse Events (CTCAE) grades, given in Table 2-3: hemoglobin, platelets, white blood cell count, neutrophils, lymphocytes, creatinine, total bilirubin (TBL), alanine aminotransferase (ALT), aspartate aminotransferase (AST), alkaline phosphatase (ALP), and others.

The number and percentage of patients with clinically notable laboratory results after baseline (Week 60E1) will also be presented by laboratory test groups and parameters listed in section 4.2. These summaries will be split into hematology and chemistry. Central and local lab results will be displayed in separate tables for clinically notable laboratory results

CTCAE v5.00 Term	Grade 1	Grade 2	Grade 3	Grade 4
HGB decreased (Anemia)	<lln 100="" a="" l<="" td="" –=""><100 – 80 a/L	<80 g/L	Life-threatening consequences; urgent intervention indicated	</lln>	<100 – 80 a/L	<80 g/L	Life-threatening consequences; urgent intervention indicated
Platelet count	<lln 75.0<="" td="" –=""><75.0 - 50.0	<50.0 - 25.0		</lln>	<75.0 - 50.0	<50.0 - 25.0	
decreased	x10e9 /L	x10e9 /L	x10e9 /L	<25.0 x 10e9 /L
White blood cell decreased	<lln -="" 3.0="" x
10e9 /L</lln>	<3.0 - 2.0 x 10e9 /L	<2.0 - 1.0 x 10e9 /L	<1.0 x 10e9 /L
Neutrophil count decreased	<lln -="" 1.5="" x
10e9 /L</lln>	<1.5 - 1.0 x 10e9 /L	<1.0 - 0.5 x 10e9 /L	<0.5 x 10e9 /L
Lymphocyte count decreased	<lln -="" 0.8="" x
10e9/L</lln>	<0.8 - 0.5 x 10e9 /L	<0.5 - 0.2 x 10e9 /L	<0.2 x 10e9 /L
Creatinine increased	>ULN - 1.5 x ULN	>1.5 - 3.0 x ULN	>3.0 - 6.0 x ULN	>6.0 x ULN
TBL increased	>ULN - 1.5 x ULN	>1.5 - 3.0 x ULN	>3.0 - 10.0 x ULN	>10.0 x ULN
ALT increased	>ULN - 3.0 x ULN	>3.0 - 5.0 x ULN	>5.0 - 20.0 x ULN	>20.0 x ULN
AST increased	>ULN - 3.0 x ULN	>3.0 - 5.0 x ULN	>5.0 - 20.0 x ULN	>20.0 x ULN
ALP increased	>ULN - 2.5 x ULN	>2.5 - 5.0 x ULN	>5.0 - 20.0 x ULN	>20.0 x ULN
GGT increased	>ULN - 2.5 x ULN	>2.5 - 5.0 x ULN	>5.0 - 20.0 x ULN	>20.0 x ULN
INR increased	>1.2 - 1.5 x	>1.5 - 2.5	>2.5	-

Table 2-3 CTCAE grades for laboratory parameters to be analyzed

Shift tables will be presented comparing baseline laboratory result (CTCAE grade) with the worst results (expressed in CTCAE grade) during the treatment phase analyzed.

